4.2 Inclusion criteria

The same inclusion criteria will be used for this COPP-IMM study as for our ongoing COPP-study.

The inclusion criteria of the COPP-study are:

- Age 0-17 years AND
 - Present to an emergency department or outpatient department of a Dutch hospital and/or be admitted to hospital
- AND
- Have at least one positive real-time RT-PCR test on nasopharyngeal, oropharyngeal, sputum or fecal sample for SARS-CoV-2 OR
 - Proof of a (recent) infection with SARS-CoV-2 by positive serology test (IgG/IgM) OR
 - Fulfil a clinical diagnosis(*) of COVID-19, should testing of SARS-CoV-2 yield inconclusive results and/or if testing is no longer possible due to lack of reagents. In these cases there must be an epidemiological link to COVID-19.

(*) This includes:

- signs, symptoms and imaging results indicative of COVID-19 pneumonia without evidence for other causes;
- inflammatory syndrome with a history consistent with recent COVID-19 AND/OR laboratory results consistent with current COVID-19 OR recent COVID-19 (e.g. positive SARS-CoV2-PCR and/or positive serology). This multisystem inflammatory disorder in children and adolescents (MIS-C) is characterized by: fever lasting at least three days, AND at least two of the following: rash or bilateral non-purulent conjunctivitis or mucocutaneous inflammation signs, hypotension or shock, features of myocardial dysfunction, pericarditis, valvulitis, or coronary abnormalities, evidence of coagulopathy, acute gastrointestinal problems, AND elevated markers of inflammation AND no other obvious microbial cause of inflammation (WHO case definition).

In addition to these general inclusion criteria for the clinical part of the study, a minimum body weight of 3 kg is required for blood sampling.

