8.1.3 Other study parameters (if applicable)

Immunological analyses will be done in cooperation with research-teams investigating adult patients with COVID-19 (eg in the BEAT-COVID1 study), so as to be able to compare hospitalized children and adults with COVID-19. Also, where possible, immune responses in hospitalized children will be compared with results from pediatric population-based studies.

We will perform similar immunological analyses in children included in the follow-up study COPP-2 (multi-center study in which children included in the COPP-study will be invited 6-12 months after presentation for a multi-disciplinary follow-up assessment).

The PedsQL and TAPQOL questionnaires measure Health Related Quality of Life at 12 weeks after diagnosis. To measure overall health and specific domains of functioning (anxiety, depression, peer relationships, sleep problems, anger, and neurocognitive functioning, anger and fatigue), we will use the PROMIS items in children older than 8 years of age. Patients admitted to the intensive care unit undergo neuropsychological evaluation as standard care in most Dutch academic centres, 3-6 months after admittance to the intensive care unit. We ask parents and patient for permission to retrieve these results.

The outcome of these psychosocial and Quality of Life evaluations will be analysed together with the detailed clinical parameters of our participants in the COPP and COPP-IMM study to examine possible risk factors for reduced quality of life or neuropsychological outcomes after COVID-19 or MIS-C.

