10. STATISTICAL ANALYSIS

10.1 Primary study parameter(s)

Statistical analysis of the primary objective: immunological profiling of children with COVID-19 or MIS-C:

1. Relative distributions of immune cell subsets will be obtained by multicolor flow cytometry. Data will be imported in R for statistical analysis. Cytosplore will be used for clustering and dimensionality reduction (9). Distributions will be compared to available reference values (normal distribution of immune cell subsets in children, adjusted for age) and will be compared across subgroups (mild COVID-19, moderate to severe COVID-19 and MIS-C).
2. Cytokine levels will be analyzed in R and SPSS. Levels will likely be non-normally distributed, in which case non-parametric Kruskal-Wallis tests will be done for comparison across groups. To adjust for multiple testing, we will use the two-stage step-up method of Benjamini *et al* (10). Cytokine levels will be compared to normal values as already available for healthy adults, and across the subgroups(mild COVID-19, moderate to severe COVID-19 and MIS-C).
3. Levels of neutralizing antibodies will be compared across subgroups (mild COVID-19, moderate to severe COVID-19 and MIS-C) using ANOVA in SPSS.

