11.4 Benefits and risks assessment, group relatedness

Subjects do not benefit personally from study participation. This non-therapeutic research with minors will have negligible risks and minimal burden. This study can only be performed in minors, as it will provide age-specific data that cannot be obtained otherwise.

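### Children's cytokine levels are set against healthy-adult normal values, so in that one comparison age cannot be separated from disease

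*Protocol*

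**What the plan says.** Section 4.2 sets the age range: "Age 0-17 years AND". No adults are enrolled.

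Section 10.1 describes the analysis of the primary objective and treats two kinds of read-out differently.

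- Item 1, immune cell subsets: the reference is the "normal distribution of immune cell subsets in children, adjusted for age".
- Item 2, cytokines: "Cytokine levels will be compared to normal values as already available for healthy adults". The same sentence adds a second comparison, "across the subgroups(mild COVID-19, moderate to severe COVID-19 and MIS-C"). For non-normal data, "non-parametric Kruskal-Wallis tests will be done for comparison across groups"; for multiplicity, "we will use the two-stage step-up method of Benjamini" and colleagues.

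Item 2 mentions neither an age adjustment nor a healthy paediatric cytokine reference. Section 8.1.3 foresees a comparison with paediatric population-based studies, but only where possible, and it names neither cytokines nor healthy children. The two example cohorts in Section 10.3 are both infected. Adult values are thus the only uninfected reference that the protocol states for cytokines.

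**The concern.** Within one section the protocol accepts that normal immune values depend on age (item 1) and then uses an adult reference for the other large set of measurements (item 2), without giving a reason. Section 11.4 defends non-therapeutic research in minors on the ground that "it will provide age-specific data that cannot be obtained otherwise". That sentence sets no rule for reference values, but an adult yardstick fits poorly with it.

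At stake is any statement that a cytokine is high, low or normal in these children. If healthy children differ from healthy adults on an analyte, the comparison mixes that difference with the disease effect. It can create an apparent abnormality, or hide a real one if the two run in opposite directions. This is a bias: recruiting more children only makes the wrong answer more precise.

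**Working it through.** **The plan's own figures.** The protocol states no alpha, power or effect size, so there is no power figure to reproduce. Its expected numbers are consistent: 60 children × about 50% consent = 30 (Section 4.1), and 10 MIS-C + 10 moderate to severe + 10 mild = 30 (Section 4.4). The illustration uses n = 10 and n = 30 for that reason.

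**What each comparison estimates.** For one analyte, let *a* be the mean difference between healthy children and healthy adults, and *s* the disease effect in a subgroup.

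- Against adult normals: expected difference = *a* + *s*. Only the sum can be estimated, because no healthy child and no diseased adult enters the comparison.
- Between two paediatric subgroups: (*a* + *s*₁) − (*a* + *s*₂) = *s*₁ − *s*₂. A common shift cancels.
- Against a paediatric reference of suitable age: *a* = 0, leaving *s*.

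**Illustration against a fixed adult norm.** Assumptions: *s* = 0, a shift of d SD, normal data, one-sample two-sided t-test at 5%, no multiplicity adjustment. Rejection probability = P(|T| > t₀.₉₇₅,ₙ₋₁), where T is noncentral t with n − 1 degrees of freedom and noncentrality d√n.

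| n | critical t | d | d√n | rejection |
|---|---|---|---|---|
| 10 | 2.262 | 0 | 0 | 5% |
| 10 | 2.262 | 0.5 | 1.58 | 29% |
| 10 | 2.262 | 1.0 | 3.16 | 80% |
| 30 | 2.045 | 0 | 0 | 5% |
| 30 | 2.045 | 0.5 | 2.74 | 75% |
| 30 | 2.045 | 1.0 | 5.48 | about 100% |

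For a wider range of d, n = 10 gives 11% at d = 0.25 and 62% at d = 0.8; n = 30 gives 26% and 99%.

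**Does false-discovery control help?** Section 8.1.1 plans more than 100 analytes. A simulation took 100 independent analytes, 30 children and 30 sampled adults, no disease effect, the same shift on every analyte, Kruskal-Wallis tests, and the two-stage step-up method at an assumed 5% level (the protocol gives no level), over 60 runs.

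| d | children v. adults, unadjusted rejection | flagged of 100 after adjustment | three child subgroups, unadjusted rejection | flagged of 100 after adjustment |
|---|---|---|---|---|
| 0 | 4.9% | 0.07 | 4.5% | 0.02 |
| 0.5 | 47% | 34 | 5.3% | 0 |
| 1.0 | 97% | about 100 | 4.6% | 0.02 |

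The adjustment works as designed when d = 0. It cannot help when d is not 0, because the child-adult difference it then detects is real; the error lies in attributing that difference to disease. The subgroup columns confirm that a common shift cancels.

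**The case against.** The strongest reply is that little of the planned inference uses the adult values. The sentence that names them also compares cytokines across the three paediatric subgroups. Section 10.2 analyses objective 2 by Kruskal-Wallis tests on drug-targetable cytokines and by hierarchical clustering of patients, and names no adult reference for either. Objective 3 is a comparison across patient groups. The second-tier examples in Section 8.1.1 contrast children with children. A reader might infer that the choice of therapeutic targets rests on the adult comparison; the stated analyses do not support that. This part of the reply stands.

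Three more stretches should be resisted.

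- One might infer that every child-adult difference will be reported as a disease effect. The protocol does not say how departures from adult normals will be interpreted, and the comparison may be meant descriptively.
- One might infer that the adult values come from a different assay run. The protocol says only that they already exist, not how or where they were measured, and Section 8.1.3 describes cooperation with teams studying adults.
- One might treat the percentages as error rates of the plan. They rest on an assumed shift and, in the first table, on a test that the protocol does not name, without the planned multiplicity control. The simulated counts assume that every analyte is shifted.

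It can also be said that the study is exploratory and has no formal sample size. That lowers the stakes but does not make the comparison interpretable. Nor is this a detail left to a later analysis plan, since the protocol itself fixes the adult reference.

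**Conclusion.** The point holds in a limited form. Of the two cytokine comparisons in Section 10.1 item 2, the one with normal values fully confounds age with disease, and it departs from the age-adjusted standard of item 1. It cannot show whether a cytokine is abnormal for a child with COVID-19 or MIS-C, in either direction, and neither sample size nor false-discovery control repairs it.

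The paediatric subgroup comparisons, objective 3 and the analyses stated for objective 2 are not affected by a shift common to all children. Age imbalance between the subgroups would be a separate matter. Such contrasts show which group is higher, however, and not whether a level departs from that of uninfected children; for that question the adult values are the only stated reference.

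The size is unknown, because the documents give neither the magnitude nor the sign of the shift. The rejection rates of 29% to about 100%, for assumed shifts of 0.5 to 1.0 SD, show only that a moderate shift would matter at the planned numbers.

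**What to change.** Reword Section 10.1 item 2 as follows.

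1. Compare cytokine levels with age-appropriate paediatric reference values on a comparable assay where these can be obtained, mirroring item 1. The paediatric population-based studies of Section 8.1.3 are one possible source, if they turn out to cover cytokines in uninfected children.
2. Show healthy-adult values as descriptive context only, and state that they support no inference about disease.
3. If no paediatric reference can be obtained for an analyte, rest inference for it on the comparisons across the paediatric subgroups.

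COPP-2 samples may supplement this but cannot be the healthy reference. Those children have been ill ("We will perform similar immunological analyses in children included in the follow-up study COPP-2", 6 to 12 months after presentation). Pairing the same child is not established either: COPP-2 invites children from the COPP-study, while Section 8.1 has 17 hospitals join COPP-IMM instead of COPP.

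The cost is a change of wording, plus the work of obtaining paediatric values. A paediatric reference may cover only some of the more than 100 analytes, and statements that a cytokine is raised will have to be more cautious. With a suitable reference and no disease effect, the rejection rate in the illustration returns to the nominal 5%.

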10.2 Secondary study parameter(s)

Secondary objectives:

- (1) To correlate the immunological profiles with detailed clinical parameters
Adjusted relative risks for specific outcome measures (such as the need for supplemental oxygen, ICU admission, duration of hospital stay) in association with immunological profiles will be calculated using logistic regression.
- (2) To determine if there are immunological targets of therapy for children with severe COVID-19 or MIS-C: Evaluate the levels of certain drug-targetable cytokines using Kruskal-Wallis tests in SPSS (eg IFN-gamma, IL-1beta, TNF-alpha) and perform agglomerative hierarchical clustering using average linking (Between Groups) with squared Euclidean distance to determine subgroups of patients with specific inflammatory profiles..
- (3) To determine if hyperinflammation in MIS-C is different from the inflammatory response in severe pediatric COVID-19: non-parametric Kruskal-Wallis tests will be done for comparison across groups (in R and SPSS).

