2. OBJECTIVES

Primary Objective:

To obtain a detailed immunological profile of children presenting to Dutch hospitals with acute SARS-CoV-2 infection or with a SARS-CoV-2 related post-infectious inflammatory syndrome (MIS-C).

Secondary Objectives:

(1) To correlate the immunological profiles with detailed clinical parameters as obtained in our related cohort study 'Clinical features of COVID-19 in Pediatric Patients' (COPP-study).

Clinical parameters include:

- severity of disease
- underlying illnesses
- age at presentation
- clinical syndrome
- laboratory parameters as obtained in routine clinical care
- clinical outcome: days of hospitalization, life-saving interventions, ICU admissions, death, patient reported outcome measures at 6 weeks follow-up.

(2) To determine if there are immunological targets of therapy for children with severe COVID-19 or MIS-C

(3) To determine if hyperinflammation in MIS-C is different from the inflammatory response in severe pediatric COVID-19.

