4. STUDY POPULATION

4.1 Population (base)

Currently, 53 hospitals are participating in the COPP-study. From April through December 2020, there have been 157 inclusions (with some children included twice if they were transferred between hospitals). Of the 48 COPP-sites, 13 have currently expressed interest in participating in the COPP-IMM study, including five academic centers. The exact number of children that will be included in COPP-IMM depends on the course of the epidemic, but based on this data, we expect to be able to include about 60 children for the observational part of the study. We expect to be able to obtain informed consent for blood withdrawal in ~50% of these patients, so 30 patients.

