4.4 Sample size calculation

A formal sample size calculation cannot be done, since it is currently unknown what the variation in immunological response is children with COVID-19 or MIS-C and how this relates to outcome measures. Based on the number of participating sites and the inclusion rate in the first wave of the epidemic, we expect to be able to include at least 60 children in total, and 30 children for the immunological part of the study.

We expect the rate of consent for blood withdrawal to be higher in patients with more severe disease (since the blood can be taken during routine blood withdrawal and no separate venapuncture will be needed). Therefore, based on inclusion rates for the related COPP-study, we estimate we will be able to include at least 10 patients with MIS-C, 10 patients with moderate to severe COVID-19 and 10 patients with mild COVID-19. Clinical information will be available for all of the patients included in the immunological part of the study.

If we will have reached 60 inclusions for the immunological part of the study within the first 18 months of the study, we will do an interim analysis to determine if more inclusions are needed. Since this is an exploratory study, no formal maximal number of inclusions can be given, but based on previous inclusions in de COPP-study and the expected course of the epidemic we do not expect to reach a higher inclusion than 60 in this timeframe.

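### Section 10.2(1) promises relative risks from logistic regression in a sample expected to be selected on the outcome: the odds ratio survives that selection, a relative risk does not

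*Protocol*

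**What the plan says.** - **Effect measure and model (Protocol 10.2, objective 1).** The plan is to report "Adjusted relative risks for specific outcome measures (such as the need for supplemental oxygen, ICU admission, duration of hospital stay"), and these "in association with immunological profiles will be calculated using logistic regression".
- **Who is sampled (4.1, 4.4).** The clinical part is sized as "we expect to be able to include about 60 children for the observational part of the study". For blood: "We expect to be able to obtain informed consent for blood withdrawal in ~50% of these patients, so 30 patients". Section 4.4 adds "We expect the rate of consent for blood withdrawal to be higher in patients with more severe disease", the reason being "since the blood can be taken during routine blood withdrawal and no separate venapuncture will be needed". It then expects "at least 10 patients with MIS-C, 10 patients with moderate to severe COVID-19 and 10 patients with mild COVID-19".
- **What severity means (8.1.2).** Severity is given in terms of the need for supplemental oxygen, which is also the first outcome named in 10.2(1).
- **Children without a sample (8.1, 8.3).** Families may join the clinical part only. Those children's data go into the same Castor database. Locally stored samples may be used, where they exist, if consent for extra sampling was not given.
- **Target (2).** "To obtain a detailed immunological profile of children presenting to Dutch hospitals".

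**The concern.** An immunological profile exists only for children with a sample, so the model in 10.2(1) can be fitted only in them. The protocol itself expects children with the outcome to be over-represented there. Odds ratios and relative risks behave differently under such selection. An odds ratio is unchanged when selection depends on the outcome alone, as in a case-control study. A risk, and hence a ratio of risks, is not.

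Section 10.2(1) names a model that yields odds ratios and promises a measure that this sampling does not preserve. A reader of the final report could take the published figure as the relative risk of needing oxygen or intensive care for a given immune profile among the children in the cohort. It would not be that figure on either reading of the sentence.

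**Working it through.** **1. The plan's own figure.** 60 × 0.50 = 30, and 10 + 10 + 10 = 30. The expected number with a blood sample reproduces. The protocol gives no consent rates by severity and no outcome risks, so everything below that needs them is illustrative.

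**2. General effect of selection on the outcome.** Let p be the true risk, and s1 and s0 the sampling fractions with and without the outcome. The risk in the sample is p·s1 / (p·s1 + (1 − p)·s0). The odds in the sample are the true odds × s1/s0. The factor s1/s0 cancels in an odds ratio but not in a ratio of risks.

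Example (assumed): risks 0.20 and 0.40, s1/s0 = 2.
- Cohort: RR = 0.40/0.20 = 2.00; OR = (0.40/0.60)/(0.20/0.80) = 2.67.
- Sample: risks 0.40/(0.40 + 0.80) = 0.33 and 0.80/(0.80 + 0.60) = 0.57; RR = 1.71; OR = 2.67.

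Over other assumed values, a true RR of 2.0 becomes:

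| s1/s0 | baseline risks | RR in sample |
|---|---|---|
| 1.5 | 0.1 to 0.4 | 1.91 to 1.71 |
| 2 | 0.1 to 0.4 | 1.83 to 1.56 |
| 3 | 0.2 to 0.4 | 1.56 to 1.38 |

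The odds ratio is unchanged in every row. A simulation of 2,000,000 children under the example gave RR 2.01 in the full cohort, 1.73 in the sample and 2.02 after inverse-sampling weighting. The OR was 2.69 in the full cohort and 2.70 in the sample.

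**3. An illustration tied to the protocol's counts.**

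Inputs from the protocol: 60 children (4.1); 10/10/10 sampled (4.4, taken as exact); 60 of 223 COPP inclusions suggestive of MIS-C (section 1).

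Assumptions: the COPP share applies here; moderate to severe COVID-19 is sampled at the MIS-C rate; the outcome coincides with the moderate to severe group; a high profile is present in 70% of moderate to severe and 30% of mild COVID-19.

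- MIS-C: 60 × 60/223 = 16.14 children, of whom 10 are sampled, 62%.
- Moderate to severe: 16.14 by assumption. Mild: 60 − 2 × 16.14 = 27.71, of whom 10 are sampled, 36%.
- Cohort, COVID-19 only. High profile: 0.7 × 16.14 = 11.30 severe and 0.3 × 27.71 = 8.31 mild, risk 0.58. Low profile: 4.84 severe and 19.40 mild, risk 0.20. **RR = 2.88.**
- Sample. High profile: 7 severe and 3 mild, risk 0.70. Low profile: 3 severe and 7 mild, risk 0.30. **RR = 2.33**, about 20% lower on the log scale (0.847 against 1.059).
- OR in the sample: (0.7/0.3)/(0.3/0.7) = **5.44**. It is the same in the cohort.
- Weighted sample, with weights 1.614 (severe) and 2.771 (mild): the cohort counts are recovered, so RR = 2.88.

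**4. Sensitivity to the assumed MIS-C share (70%/30% profile).**

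| MIS-C share | cohort RR | RR converted in sample | OR labelled as RR |
|---|---|---|---|
| 20% | 3.50 | 2.33 | 5.44 |
| 27% | 2.88 | 2.33 | 5.44 |
| 33% | 2.33 | 2.33 | 5.44 |

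At 20% the groups are 12, 12 and 36, so the cohort risks are 8.4/19.2 = 0.4375 and 3.6/28.8 = 0.125. At one third each group has 20 children, all are sampled at 50%, and the selection effect is nil. The labelling error remains in all three rows.

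At the 27% share, other assumed profile prevalences (60/30, 80/20, 60/40) lose 19 to 21% on the log scale.

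**The case against.** The strongest reply is that the planned model is logistic regression, and its coefficient is an odds ratio that this selection leaves alone. That stands. A reader might infer that the planned regression is itself biased towards 1 by severity-dependent consent. The documents do not support this: the pull towards 1 arises only if risks in the sampled children are turned into relative risks, a step 10.2 does not describe. But if no such step is taken, an odds ratio is being called a relative risk, and the error runs the other way. The sentence does not deliver a cohort relative risk either way.

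Other points that stand:

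- **Weighting.** A reader might infer that the analysis will be unweighted. The protocol is silent, and an analysis plan that is not shown could deal with it. The fault is the stated effect measure, not the silence.
- **Pooled results.** It is tempting to add that overall profiles or cluster frequencies are tilted towards severe disease. No pooled mean, absolute risk or cluster prevalence is planned. Sections 10.1 and 10.2(3) compare groups, and 10.2(2) uses clustering to find subgroups. Severity-dependent sampling does not by itself bias comparisons between severity groups.
- **Size.** The 10/10/10 are floors, 4.4 speaks of at least 60 children, and the sampling fractions and prevalences are assumed. The protocol's counts alone do not yield the 20% loss.
- **Stored samples.** They may add children who did not consent to extra blood (8.3, item 5), so the sampled set is not simply the consenting half. They are used only where they exist, and 4.4 ties routine draws to more severe disease, so they need not remove the selection.

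One limit cuts against the odds ratio too. If sampling also depends on the profile given the outcome, the odds ratio is no longer protected; in one simulated example it fell from 2.69 to 1.88. The documents do not say whether this would happen.

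**Conclusion.** The point holds as a wrong choice of effect measure in 10.2(1). By the protocol's own account, inclusion depends on severity, and severity is defined by one of the modelled outcomes. A relative risk converted from the sampled children would be too close to 1. An odds ratio labelled as a relative risk would be too large, since the outcomes are common (37%, or 16.14 of 43.85 children with COVID-19, in the illustration).

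The direction of the first error follows from 4.4 and 8.1.2. Its size cannot be fixed from the documents and is zero if sampling fractions turn out equal across groups. Under the stated assumptions, about 2.9 in the cohort becomes 2.3 or 5.4.

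This concerns a secondary, exploratory objective. It does not touch the primary group comparisons.

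**What to change.** **Preferred.** In 10.2(1), replace relative risks with adjusted odds ratios for the binary outcomes, and state that no absolute or relative risks will be reported from the sampled children. This is a change of wording and needs no new data. The odds ratios should not be described as risk ratios in the report.

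**If relative risks are wanted.** Use a model that yields them, such as log-binomial or Poisson regression. Weights in a logistic model still give an odds ratio. Weight each sampled child by the inverse of the sampling fraction in its group (mild, moderate to severe, MIS-C): children in the clinical part divided by children with a sample, both from Castor. Use robust standard errors.

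The cost is one paragraph and some variance. The design effect n·Σw²/(Σw)² is 30 × 10 × (2 × 1.614² + 2.771²)/60² = 1.07 under the illustration, and 1.32 with an MIS-C share of 20%. The weighted result carries over to the COPP-IMM clinical cohort, meaning consenting children at the participating hospitals, and not to all children presenting to Dutch hospitals. It does not correct selection on the profile within a severity group.

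**Either way.** Report the characteristics of sampled and unsampled children side by side. Sections 10.1 and 10.2(3) stay as they are.

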8.1.2 Secondary study parameters/endpoints (if applicable)

We will correlate the immunological profiles with detailed clinical outcome measures of the patients. We will collect these clinical outcome measures in the same manner as in our related cohort study 'Clinical features of COVID-19 in Pediatric Patients' (COPP-study). Clinical parameters collected include: severity of disease (need of supplemental oxygen); underlying illnesses; age at presentation; clinical syndrome; laboratory parameters at diagnosis and during illness; response to treatment; clinical outcome: days of hospitalization, life-saving interventions, ICU admissions, death, patient reported outcome measures at 6 weeks follow-up.

Also, we will explore if there are potential immunological targets of therapy for children with severe COVID-19 or MIS-C, and if immunological profiles differ between MIS-C and severe pediatric COVID-19.

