10.3 Other study parameters

Comparison between immunological profiles of hospitalized children with COVID-19 and other cohorts (eg adults with severe COVID-19, non-admitted children with COVID-19) will be done using parametric (ANOVA) or non-parametric (Kruskal-Wallis) tests were applicable, depending on whether the data is normally distributed or not. Logistic regression will be used to determine associations between clinical parameters and the results from the questionnaires on Quality of Life and functioning.

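### Section 10.2 promises adjusted relative risks from logistic regression, which yields odds ratios, and applies it to length of stay, which is counted in days and has no stated cut-off

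*Protocol*

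**What the plan says.** Section 10.2, under secondary objective 1, names the effect measure and the outcomes together: "Adjusted relative risks for specific outcome measures (such as the need for supplemental oxygen, ICU admission, duration of hospital stay"). The sentence continues "in association with immunological profiles will be calculated using logistic regression".

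Section 8.1.2 gives the scale of the outcomes: "clinical outcome: days of hospitalization, life-saving interventions, ICU admissions, death, patient reported outcome measures at 6 weeks follow-up". Section 2 also lists length of stay as days. The protocol gives no cut-off for days in hospital, no ordinal model, and no step that turns an odds ratio into a relative risk.

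Section 10.3 uses the same model for the questionnaires: "Logistic regression will be used to determine associations between clinical parameters and the results from the questionnaires on Quality of Life and functioning". On the instruments, Section 8.1.3 says: "The PedsQL and TAPQOL questionnaires measure Health Related Quality of Life at 12 weeks after diagnosis". It adds PROMIS items for children older than 8 years and gives the aim as "to examine possible risk factors for reduced quality of life or neuropsychological outcomes after COVID-19 or MIS-C".

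**The concern.** The measure and the model in Section 10.2 do not match. For a binary outcome the coefficient from logistic regression is a log odds ratio. It approximates a relative risk only when the outcome is rare, and oxygen need is unlikely to be rare in this sample. For a count of days the model cannot be fitted until someone picks a threshold. A threshold chosen after the data are seen adds analytic freedom and discards information.

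This is the only model that the protocol gives for relating immune profiles to clinical outcome. Estimates labelled as relative risks that are really odds ratios would make the immune markers look more strongly tied to severity than they are.

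The word risk raises a smaller, related issue. Blood is drawn after diagnosis and consent (Section 8.3), and families have at least 24 hours to decide (Section 11.2). Oxygen or ICU admission can therefore come before the sample, and an association with an earlier event is not a risk.

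**Working it through.** **The plan's own figure.** The protocol states no power, event rate or effect size. Its one count reproduces: about 50% of 60 children gives 60 × 0.5 = 30 (Section 4.1), and 10 MIS-C + 10 moderate to severe + 10 mild = 30 (Section 4.4).

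**Risk of oxygen need.** Section 8.1.2 ties severity to the need for supplemental oxygen. If the moderate-to-severe group needs oxygen and the others do not, the risk is 10/30 = 33%. If every MIS-C child also needs it, the risk is 20/30 = 67%. The MIS-C definition in Section 4.2 does not include oxygen need, so 67% is an upper bound.

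**Odds ratio against relative risk.** Assume an immune marker split 15/15, overall risk r and true relative risk RR, unadjusted. Then:

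- p0 = 2r/(1 + RR) and p1 = RR × p0
- OR = [p1/(1 − p1)] / [p0/(1 − p0)]

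For RR = 2.0:

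| Overall risk r | p0 | p1 | OR | OR/RR |
|---|---|---|---|---|
| 5% | 0.033 | 0.067 | 2.07 | 1.04 |
| 10% | 0.067 | 0.133 | 2.15 | 1.08 |
| 33% | 0.222 | 0.444 | 2.80 | 1.40 |
| 50% | 0.333 | 0.667 | 4.00 | 2.00 |
| 67% | 0.444 | 0.889 | 10.0 | 5.0 |

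At 33%, an RR of 1.5 gives an OR of 1.83 and an RR of 3.0 gives 5.00. In whole counts, 10/15 against 5/15 has RR = 2.0 and OR = (10/5)/(5/10) = 4.0; the overall risk there is 15/30 = 50%.

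**Cost of cutting a continuous outcome.** For a normal score cut at c, the share of information kept is φ(c)²/[Φ(c)(1 − Φ(c))]. At the median this is 0.3989²/0.25 = 0.64. A simulation (10,000 runs, 15 against 15, assumed shift of 1 SD, two-sided 0.05) gave power of about 72% for a rank test on the full scale. After a median split analysed by a logistic likelihood-ratio test, power was about 48%.

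**The case against.** The strongest reply is that logistic regression can yield adjusted relative risks. Predicted risks from the fitted model are averaged over the sample and their ratio is taken, and the protocol nowhere says that odds ratios will be presented as relative risks. This stands in part. It would rescue oxygen need and ICU admission if Section 10.2 named the step, which it does not. It does nothing for length of stay. An analysis plan not shown here might set a cut-off, but the measure and model named in the protocol would still not fit an outcome in days.

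The size also depends on how common the outcome is. At 5 to 10% risk the gap is trivial, and no ICU rate is given.

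Three stronger readings are tempting and not supported:

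- **That 20 of 30 children have the outcome by design.** That counts membership of the MIS-C and moderate-to-severe groups. The text supports about 10 of 30 for oxygen need, more only if MIS-C children also need it.
- **That Section 10.3 makes the same error.** It promises associations, not relative risks, and the aim of studying reduced quality of life leaves room for a binary outcome. Ordinal logistic regression is not excluded. What remains is a point about efficiency.
- **That the quality-of-life analysis rests on 30 to 60 children.** Sections 8.1 and 8.1.3 pool these data with COPP, which had 223 inclusions by April 2021 (Section 1). Questionnaire response is unknown.

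On timing, Section 8.3 aims for sampling as early as possible and records its exact date and time, so the order of events can be established at analysis.

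**Conclusion.** The point holds for Section 10.2. Length of stay is the clearest part: an outcome in days is assigned a relative risk and a binary-outcome model with no threshold. For oxygen need, a true relative risk of 2.0 corresponds to an odds ratio of about 2.8 at 33% overall risk and 4.0 at 50%. This rests on three assumptions: an equal marker split, no covariate adjustment, and oxygen need tracking the planned severity groups. For ICU admission the gap cannot be sized from the protocol; it would be only about 4 to 8% if the risk were 5 to 10%.

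A reader might infer that the study's effects will necessarily be overstated. They will be only if the odds ratio is reported or read as a relative risk, though the label in Section 10.2 invites that.

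This should be fixed, but it does not threaten the study. It affects a secondary objective of an exploratory cohort, and the primary analyses in Section 10.1 do not depend on it.

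**What to change.** In Section 10.2:

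- **Oxygen need and ICU admission.** Either estimate relative risks, by modified Poisson regression with small-sample robust standard errors or by standardising the logistic fit, or keep logistic regression and report odds ratios as odds ratios. With about 10 oxygen events, use Firth penalisation in the second case. Under either option, few covariates can be carried.
- **Length of stay.** Analyse days, by a negative binomial model, a log-linear model or time to discharge. State how deaths are handled and, since outpatients are eligible, whether children never admitted count as zero days.
- **Order of events.** Use the recorded sampling date and time to separate events before and after the sample. Describe associations with earlier events as cross-sectional, not as risks.

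As a secondary suggestion for Section 10.3, analyse PedsQL, TAPQOL and PROMIS results as scores, within instrument, in the pooled COPP and COPP-IMM data. If a binary outcome is wanted, state the threshold in advance.

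The cost is wording and a little more analysis work, with no new data. Relative risks will look smaller than odds ratios, and fewer events will count as risks once those before sampling are set apart.
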